## 9.2.2 Assessment of secondary outcomes

### 9.2.2.1 *Change in the number of potentially inappropriate DDDs*

The number of DDDs for each treatment of each participant will be computed taking into account the regimen (once a day, twice a day, etc.), the dose prescribed, and the DDD for the specific medication, as specified by the WHO Collaborating Centre for Drug Statistics Methodology . The PIM status for each treatment will then be assessed as for the primary outcome, and the change between baseline and 4 follow-up computed. Some drugs and specific preparations will be excluded from this analysis, as no DDDs can be computed for them. The exclusion list can be found in Annex 15.

### 9.2.2.2 *Change in the total number of regular drugs*

The total number of regular drugs, without regard for PIM status, will be extracted from the medication plans collected for the assessment of the primary outcome. Regular drugs are defined as drugs with a fixed administration schedule, i.e. not “reserve” drugs. The change between baseline and follow-up will then be computed.

### 9.2.2.3 *Change in the total number of regular DDDs*

The total number of regular DDDs will be computed as previously described (see 9.2.2.1), without regard for PIM status, and the change between baseline and follow-up calculated.

### 9.2.2.4 *Change in health-related quality of life (using EQ-5D-5L)*

The results of the quality of life questionnaire for each quality of life dimension, as well as the measurement on the visual analogue scale, will be extracted from the questionnaire uploaded at baseline and follow-up in an investigator-reserved CRF (see Annex 12). The total score for each visit and the change between baseline and follow-up will then be computed by the investigators.

### 9.2.2.5 *Change in the number of common complaints*

The number of common complaints will be extracted from the questionnaires collected at baseline and follow-up, using an investigator-reserved CRF (see Annex 13), and the change between baseline and follow-up calculated for each participant.

## 9.2.3 Assessment of implementation outcomes

### 9.2.3.1 *Number and rate of pharmacist propositions validated by the care team, of validated propositions accepted by the participants, and of accepted propositions implemented within 4 months.*

Those 6 outcomes will be computed from the information provided on the deprescribing plans at baseline and follow-up.

### 9.2.3.2 *Drug reintroduction rate*

The drug reintroduction rate will be computed by dividing the number of drugs having been restarted at follow-up by the total number of drugs having been stopped.

### 9.2.3.3 *Satisfaction of the participants*

Ad-hoc short questionnaire currently in development

### 9.2.3.4 *Satisfaction of healthcare professionals*

Ad-hoc short questionnaire currently in development

### 9.2.3.5 *Perception of the intervention by participants' relatives*

Ad-hoc short questionnaire currently in development

### 9.2.3.6 *Time needed for the implementation of the intervention;*

Ad-hoc short questionnaire currently in development

### 9.2.3.7 *Delay between the acceptance of validated proposition by the participant and their implementation*

The time taken for implementation of accepted propositions will be extracted from the deprescribing plans at baseline and follow-up.

---

[https://www.whocc.no/atc\\_ddd\\_index/](https://www.whocc.no/atc_ddd_index/)

#### **9.2.3.8 Impact of the intervention on drug costs;**

The monthly cost of treatment for both baseline and follow-up drug treatment will be calculated based on the public price of prescribed drug on December 31st, 2018, taking into account the dose regimen. The impact of the intervention on drug costs will then be computed by subtracting the baseline costs from the follow-up for each participant.

#### **9.2.3.9 Cost of training healthcare professionals for the intervention.**

The cost of training will be calculated by multiplying the number of hours spent in training by participating pharmacists by the mean cost of employment of a pharmacist in the canton of Vaud (information to be provided by the Société Vaudoise de Pharmacie).

#### **9.2.3.10 Neuro-Psychiatric Inventory – Nursing Home**

The NPI-NH questionnaire will be extracted using an investigator reserved CRF (see Annex 14), the score will be calculated for each visit, and the difference in NPI-NH score computed by the investigators.

#### **9.2.3.11 The study refusal rate at recruitment stage and the number of participants withdrawing from the study;**

The result of each proposition to join the study will be recorded on the list of eligible residents prepared by the pharmacist (see section 7.2, page 19). Participants withdrawing from the study will be recorded on the follow-up CRF (see Annex 10).

#### **9.2.3.12 The number of calls received by of the Centre de Pharmacie Communautaire Pharmaceutical Assistance team (see 8.1.1)**

The number of calls relative the IDel study will be extracted post-hoc from the monitoring system of the CPC. No participant information will be provided to or collected by the CPC Pharmaceutical Assistance team.

### **9.2.4 Assessment of safety outcomes**

#### **9.2.4.1 Mortality rate**

All deaths will be recorded by the NH nurse responsible for the study, using the follow-up CRF. The mortality rate will then be computed by the investigators.

#### **9.2.4.2 Hospitalisation rate**

All hospitalisations will be documented by the NH nurse using the follow-up CRF, by reporting the beginning and end dates for each hospital stay. If no hospital stay occur during the trial period, the follow-up CRF will be completed accordingly. Elective hospitalisations will be excluded from analysis. The number of participants having been hospitalised will then be computed, and the hospitalisation rate calculated.

#### **9.2.4.3 Number of days spent in the hospital**

Using the dates entered in the follow-up CRF, the total number of days spent in the hospital will be computed.

#### **9.2.4.4 Causes of hospitalisation**

Causes of hospitalisation will be reported in the follow-up CRF.

#### **9.2.4.5 Number of falls**

The number of falls having occurred to each participant will be reported in the CRF for follow-up data collection. The number of falls for each group will then be computed by the investigators.

#### **9.2.4.6 Number of participants having fallen**

The number of participants having fallen will be computed by investigators using data on the number of falls.

#### **9.2.4.7 Number of falls in participants with at least one fall**

The number of falls having occurred to participants that have fallen at least once will be computed by the investigators.

#### **9.2.4.8 Number of days with use of restraints**

The number of days with use of restraints will be reported in the follow-up CRF. Restraints measures are defined as the use of mechanical restraints (bed barriers, bindings) or movement detectors placed in the participants' room (alarm bedmat).

#### 9.2.4.9 *Adverse events*

See section 10, page 26, for the reporting of adverse events.

#### 9.2.4.10 *Laboratory parameters*

No laboratory values will be collected.

#### 9.2.4.11 *Vital signs*

No vital signs will be collected.

### 9.2.5 Assessments in participants who prematurely stop the study

In case of participant death before completion of follow-up, the follow-up CRF (staged for completion at visit 2) will be completed within 7 days by the pharmacist and nurse. For the assessment of the treatment plan regarding PIM status, the pharmacist will take into account the treatment plan of the day preceding death. No information will be collected regarding quality of life and common complaints.

If a participant is hospitalised at the date of the follow-up visit, the same procedure as for the participant having died is applied. The treatment plan of the day preceding the hospitalisation will be taken into account.

If a participant wishes to stop the study before the follow-up visit, she/ he will be offered to complete the quality of life and common complaints questionnaire before exiting the study.

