## **7.4 Criteria for withdrawal of participants**

Participants, or their representative if applicable, can withdraw from the study at any time, without justification.

The NH care team can withdraw participants from the study if they estimate that the safety of the participant is not guaranteed anymore. However, we do not anticipate this to happen: if the clinical status of the participant does not allow for treatment alterations, the NH care team will simply not enact the planned treatment modifications. In addition, a stopped or tapered drug can be reintroduced at any time during the study. The treating physician will indeed remain in control of the participant's care at all time.

Participants withdrawing during the study will not be replaced.

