### 11.4 Planned Analyses

#### 11.4.1 Datasets to be analysed, analysis populations

The analyses will be performed following the intention to treat approach.

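### A living resident in hospital on the Visit 2 date is closed out by the death procedure, so drug changes during the stay are left out of the 4-month PIM count and the questionnaires are lost

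*Combined protocol and SAP*

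**What the plan says.** Section 9.2.5 sets the procedure after a death: "the follow-up CRF (staged for completion at visit 2) will be completed within 7 days by the pharmacist and nurse". For the PIM count, "the pharmacist will take into account the treatment plan of the day preceding death". For the questionnaires: "No information will be collected regarding quality of life and common complaints".

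The section then extends this to the living: "If a participant is hospitalised at the date of the follow-up visit, the same procedure as for the participant having died is applied". The only adaptation is the reference day: "The treatment plan of the day preceding the hospitalisation will be taken into account".

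Neither 9.2.5 nor 9.3.2 describes a deferred visit, a visit window or an assessment after discharge. Section 9.3.2 places Visit 2 at 16 weeks after Visit 1 and has the current medication plan uploaded then.

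Related provisions:

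- Section 7.4 says that "a stopped or tapered drug can be reintroduced at any time during the study".
- Section 9.2.3.2 takes the reintroduction rate from the drugs that have been restarted at follow-up.
- Section 9.2.4.2 documents hospitalisations "by reporting the beginning and end dates for each hospital stay".
- Section 11.4.1: "The analyses will be performed following the intention to treat approach".
- Section 11.5 provides multiple imputation for missing outcome data only, and section 11 plans no sensitivity analysis.

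**The concern.** After a death there is no later regimen to measure, so the last plan in life is a natural choice. A resident in hospital at week 16 is in a different position: alive, still enrolled, and possibly back in the NH soon. Three things follow from treating the two alike.

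1. **The primary outcome can miss the result of a withdrawal.** The endpoint is change to 4 months, but the regimen scored is that on the eve of admission. A withdrawn drug restarted in hospital is not in the count. If the failed withdrawal led to the admission, the resident is scored as a PIM reduction.
2. **Similar residents are scored on different bases.** One in hospital during weeks 13-15 is back by week 16 and is scored on the post-hospital plan. One in hospital during weeks 15-17 is scored on the pre-hospital plan. The calendar alone decides.
3. **Secondary outcomes are lost without need.** EQ-5D-5L and common complaints are secondary outcomes 5 and 6, and the synopsis lists quality of life among the main secondary outcomes. Section 9.2.5 offers both questionnaires to a resident who leaves the study early, but not to an enrolled resident who is temporarily in hospital. Because the loss is tied to hospitalisation, the missing-at-random condition in section 11.5 is doubtful for these data.

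**Working it through.** **1. Which drug changes are missed.** Setting 9.2.5 against 9.3.2 and 7.4:

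| Event | In the 4-month PIM count? |
|---|---|
| Drug restarted in the NH before admission | Yes, it is in the pre-admission plan |
| Drug restarted in hospital, resident back by week 16 | Yes if still prescribed, as the current plan is scored |
| Drug restarted in hospital, resident still there at week 16 | No |
| PIM stopped in hospital, resident still there at week 16 | No, the PIM is still counted |

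The gap is confined to changes made during a stay that spans the visit date, and it runs both ways.

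**2. Whether anything later corrects it.** The pre-admission value enters as an observed value, so imputation under 11.5 does not touch it. No sensitivity analysis is planned. The reintroduction rate may miss the same restart, because 9.2.5 gives no reference date for the updated deprescribing plan.

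**3. Hospital days.** Section 5.4 counts days from baseline to completion of the follow-up period, and 9.3.2 puts follow-up at 16 weeks (16 x 7 = 112 days). Days after that fall outside the window for every participant. A stay counted up to Visit 2 therefore loses 0 days. What is missing is an instruction for a stay with no end date yet, and a statement of when the 7 days for the CRF start in a living resident.

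**4. Number affected.** The plan's own projection (section 11.2) reproduces: half of 18 NHs = 9, and 9 x 59 beds x 0.20 = 106.2, or 106. With 1:1 allocation (6.2.1) that is about 53 per arm. The documents give no hospitalisation rate, so I assume 1-3% of residents are in hospital on a given day:

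- both arms: 106 x 0.01 = 1.1 to 106 x 0.03 = 3.2 residents;
- intervention arm: 53 x 0.01 = 0.5 to 53 x 0.03 = 1.6 residents.

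**5. Effect on the arm mean.** Shift = (residents in hospital at Visit 2 x PIMs restarted per resident) / 53.

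- One resident, one restart: 1 / 53 = 0.02 PIM.
- Three residents, one restart each: 3 / 53 = 0.06 PIM.
- Five residents (9.4% of the arm), two restarts each: 10 / 53 = 0.19 PIM. This is a deliberately wide upper case.

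**6. Effect on the reintroduction rate.** Shift = missed restarts / (53 x drugs stopped per resident), with 1 to 3 drugs stopped per resident assumed and one missed restart per hospitalised resident.

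- Smallest: 1 / (53 x 3) = 0.6 percentage points.
- Largest: 5 / (53 x 1) = 9.4 percentage points.

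**The case against.** The rule can be defended. Section 12.1.2 makes the NH record the source for the medication plan. The last NH regimen keeps acute inpatient prescribing out of the count and keeps the resident in the analysis, which fits the intention-to-treat statement. A deferred visit would measure the regimen some weeks after the stated 4 months and would bring in hospital-driven changes unrelated to the intervention. This is a fair reason not to score the inpatient chart. It is weaker against scoring the plan in force once the resident is back in the NH, because that is already how residents discharged before week 16 are scored.

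Two further points stand. The harm is not hidden: a non-elective admission counts in the hospitalisation rate (9.2.4.2) and its cause is recorded (9.2.4.4). If a causal link with the intervention cannot be excluded, it is a serious adverse event and is reported (10.1, 10.2.1). The chain needed for a bias is also long: a failed withdrawal causes an admission, the stay spans week 16, the drug is restarted there, and it counts as a PIM.

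A reader might also infer that the ongoing stay is cut short, so that hospital days are undercounted in favour of the intervention. Section 5.4 does not support this, since the count ends with follow-up for everyone. Nor does 9.2.5 count the resident as dead; it borrows the data-collection procedure, and the mortality rate is unaffected.

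**Conclusion.** The concern holds as a measurement rule that should be changed, not as a demonstrated bias. For a living resident in hospital at Visit 2, the plan scores an out-of-date regimen as the observed primary outcome, treats that resident differently from one discharged shortly before, and gives up two secondary outcomes that could be collected later.

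The size is small. At an assumed 1-3% in hospital on a given day, about 1 to 3 of 106 residents are affected across both arms, and each missed restart moves an arm mean by 0.02 PIM. Wider assumptions reach 0.19 PIM. The documents supply none of the rates behind these figures.

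It is tempting to conclude that the rule favours the intervention. It does in the single case of a failed withdrawal restarted in hospital. But it applies to both arms and also ignores PIMs stopped in hospital or added to controls, so the net direction is not established. The reason to act is that these few residents are especially informative about harm and the change is cheap.

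**What to change.** In section 9.2.5, separate living hospitalised residents from deaths:

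- Hold Visit 2 (treatment plan, EQ-5D-5L, common complaints, NPI-NH) on return to the NH, within a stated window, for example up to 4 weeks after week 16. Score PIMs on the plan in force at that visit, and date the updated deprescribing plan the same way.
- Use the pre-admission plan only if the resident has not returned by the end of the window or dies.
- Count all safety outcomes to day 112 in everyone, with a stay still open counted to that day, so that a later visit adds no exposure time.
- State when the 7 days for completing the CRF begin.
- In section 11, add a sensitivity analysis that scores these residents on the pre-admission plan.

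This changes measurement only and adds no visit. The cost is that a few primary-outcome assessments fall some weeks after week 16, and database lock may be slightly later.

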## 9.3 Procedures at each visit

As not all NH nurses and pharmacists have laptop computers or tablets at their disposal to perform the various questionnaires at each visits, the questionnaires will be completed in paper form with the participant or her/his representative, and uploaded into the CRF after visit completion. Transcription of uploaded documents will be made by the investigators into specific CRFs.

### 9.3.1 Visit 1: Baseline data collection

Timeframe: immediately after inclusion for control group; at the time of implementation of the deprescribing plan for the intervention group.

Action performed with the participant:

- Completion of the baseline EQ-5D-5L questionnaire (using the paper version), by the pharmacist and the nurse, in presence of the participant or her/his representative;
- Completion of the baseline common complaints questionnaire (see Annex 5);
- Planning of the follow-up visit.

Action performed after the visit, in the absence of the participant:

- Upload of the baseline EQ-5D-5L questionnaire into the CRF;
- Upload of the baseline common complaints questionnaire into the CRF;
- Upload of the current medication plan into the CRF;
- Performing and upload of the PIM assessment, as described in section 9.2.1;
- Upload of the deprescribing plan (see Annex 8) into the CRF;
- Completion of the NPI-NH questionnaire (see Annex 6) by the nurse referent for the participant, and upload by the pharmacist into the CRF.

### **9.3.3 Collection of implementation data**

The collection of implementation-specific data (satisfaction with the intervention, perception of participants' relatives, etc.) will happen after conclusion of follow-up. Ad-hoc questionnaires will be used for the collection of this information. Questionnaires provided to the participants' relatives about their perception of the intervention (see section 9.2.3.5, page 22) will include the participant's identification code, to enable the investigators to link these information to the objective data collected on the participant. No health-related data will be collected at this stage.

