In case of acute adverse reaction after the withdrawal of a drug, corrective measures, including reinstating the treatment, can be put into practice extremely quickly given the close monitoring of residents in NHs. The risks of stopping long-term preventive treatments (for example cholesterol-lowering drugs) are less well known; however, the benefits of such preventive drugs in the very elderly are also not well established: most preventive drug have not been studied in this population [6]. The benefits of these treatments in the adult population are, in general, expected to occur in a timeframe longer than the average life expectancy of NH residents: the mean duration of stay in the NHs of Fribourg and Vaud was less than 3 years in 2015 [34].

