#### **4.4 Implementation objectives**

Implementation objectives are to assess the acceptability, adoption, feasibility, appropriateness, penetration, fidelity, sustainability and costs of the intervention.

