### **8.5 Data Collection and Follow-up for withdrawn participants**

No further data collection will occur for participants withdrawing from the study. Data already collected will be anonymised and used in the analysis.

Withdrawn participants will be monitored as usual by the NH care team.

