#### **12.1.2 Specification of source documents**

All demographic data (age, gender, date of entry in the NH), data regarding the medication plan, hospitalisations, falls, use of restraints and death will be extracted from the participant's record in the NH, which is considered the source document.

For other data, the source documents are as follow:

- Informed consent form: paper form signed by the participant or her/his representative;
- Randomisation number: eCRF (automatically generated);
- Visit date: eCRF;
- EQ-5D-5L questionnaires: paper questionnaire filled by the participant / at the participant's bed;
- Common complaints: paper questionnaire filled with the participant / at the participant's bed;
- NPI-NH: paper questionnaire filled by the referent nurse;
- PIM assessment: electronic form obtained after analysis of the PIMS, as described in section 9.2.1;
- Deprescribing plan: paper form filled and updated by pharmacist, nurse and physician;

All source documents will be filed in a designated folder provided by the investigators; this folder will be kept in the NH nurse office.

Information specific to the implementation outcomes will be collected after the end of the study; source documents will be ad-hoc questionnaires that have yet to be developed.

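### Residents' own satisfaction is asked only after follow-up and not at early exit, so the reported figure will describe completers only and may be overstated

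*Combined protocol and SAP*

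**What the plan says.** All references are to the combined protocol and SAP.

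- **Objective.** Section 4.4 reads: "Implementation objectives are to assess the acceptability, adoption, feasibility, appropriateness, penetration, fidelity, sustainability and costs of the intervention". No outcome is assigned to any one of these constructs.
- **Outcome.** Section 5.3, item 8, lists satisfaction of participants and of healthcare professionals. Item 9 lists relatives' perception. Sections 9.2.3.3 to 9.2.3.5 say that these questionnaires are still being developed.
- **Timing.** Under section 9.3.3, collection of satisfaction and relatives' perception "will happen after conclusion of follow-up. Ad-hoc questionnaires will be used for the collection of this information". Section 12.1.2 puts it differently: "Information specific to the implementation outcomes will be collected after the end of the study".
- **Withdrawal.** Section 8.5: "No further data collection will occur for participants withdrawing from the study".
- **Early exit.** Under section 9.2.5, a resident who wishes to stop "will be offered to complete the quality of life and common complaints questionnaire before exiting the study". Satisfaction is not on that list. After a death, staff complete the follow-up form, and the section adds: "No information will be collected regarding quality of life and common complaints".
- **Analysis.** Section 11.4.2 restricts implementation outcomes to description. Section 11.5 allows multiple imputation of participant-level outcomes under a missing-at-random condition and does not say whether implementation outcomes are covered.

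**The concern.** A resident who leaves because the experience was bad is the one whose opinion of the intervention is most informative, and the plan never asks for it. The plan does foresee the problem for quality of life and common complaints, because it offers both at exit. Leaving satisfaction out of the same contact looks like an oversight.

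At stake is how the satisfaction result is read. Implementation is part of the overall objective (section 4.1). A satisfaction percentage with no stated denominator could be taken as the view of everyone who received the intervention, when it is the view of those who stayed to the end. The analysis cannot repair this afterwards. A descriptive summary makes no correction, and withdrawal driven by dissatisfaction would not meet the missing-at-random condition in section 11.5. The count of withdrawals (section 5.3, item 15) shows how many left, not what they thought.

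**Working it through.** **Step 1: who can answer.**

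| Resident's status | Satisfaction asked? | Basis |
|---|---|---|
| Alive and in the study after follow-up | Yes | 9.3.3, 12.1.2 |
| Withdraws early | No: exit step omits it, nothing collected later | 9.2.5, 8.5 |
| Dies before the end of follow-up | No: nothing is sought beforehand | 9.3.3, 9.2.5 |

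The result is restricted to completers by design.

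**Step 2: size of the group.** Section 11.2 expects half of 18 nursing homes, with a mean of 59 beds and 20% recruited: 9 × 59 × 0.20 = 106.2, which reproduces its figure of 106. With 1:1 allocation (section 6.2.1), about 53 residents are in the intervention arm. Section 6.1 uses 10 homes of 50 residents, giving 10 × 50 × 0.20 = 100, or 50 per arm. The percentages below do not depend on which is used.

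**Step 3: size of the possible bias.** The documents give no rate of withdrawal or death for this trial and no satisfaction figure, so every value here is assumed. Let *a* be the share of intervention residents lost before the questionnaire, *s* satisfaction among those who answer, and *u* satisfaction among those lost.

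- True satisfaction = (1 − a) × s + a × u
- Bias of the reported figure = s − true = a × (s − u)

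With s = 80%:

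| Share lost, a | Lost, of 53 | Bias if u = 0% | u = 40% | u = 80% | u = 100% | True value, worst to best case |
|---|---|---|---|---|---|---|
| 10% | about 5 | +8 | +4 | 0 | −2 | 72% to 82% |
| 20% | about 11 | +16 | +8 | 0 | −4 | 64% to 84% |
| 40% | about 21 | +32 | +16 | 0 | −8 | 48% to 88% |

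For the first row: 0.90 × 80 + 0.10 × 0 = 72, so the bias is 80 − 72 = +8 points; and 0.90 × 80 + 0.10 × 100 = 82, so the bias is 80 − 82 = −2 points. The sign depends entirely on whether those lost were less satisfied than those who answered.

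**The case against.** Several points on the other side stand.

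**Acceptability as a whole.** A reader might infer that acceptability is measured only in residents who stayed and survived. The documents do not support that. Section 4.4 ties acceptability to no single instrument. Section 5.3 also lists whether participants or relatives accepted the validated propositions (items 3 and 4), professionals' satisfaction (item 8), and refusals and withdrawals (item 15). Acceptance is taken from the deprescribing plans (section 9.2.3.1), the first of which is uploaded at Visit 1. Refusals are logged on the recruitment list and withdrawals on the follow-up form (section 9.2.3.11). None of these requires the resident to finish. They do not replace the missing opinion, however: acceptance is given before the plan is put into practice (section 6.1).

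**Relatives.** Section 9.3.3 sets when relatives are asked and excludes no one. Relatives of residents who died are not ruled out.

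**Certain overstatement.** A reader might also infer that satisfaction will be overstated, and might size this from section 3.4, where "the mean duration of stay in the NHs of Fribourg and Vaud was less than 3 years in 2015". Under a constant exit rate, 1 − exp(−4/36) = 10.5% would have left by 4 months and 1 − exp(−6/36) = 15.4% by 6 months; a shorter mean stay would raise both. But this is turnover of all residents, including deaths. It is not withdrawal from the study through dissatisfaction, and nothing in the documents links death to dissatisfaction. The 6-month figure also includes up to 2 months before the plan is implemented. Giving that whole group a low satisfaction rate would not be justified.

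**Staying while dissatisfied.** Each item of the plan is put to the resident or representative for approval (section 6.1). Changes can be left undone and drugs restarted (section 7.4). An unhappy resident can refuse or reverse the changes, remain in the study and answer the questionnaire. This may keep the loss small, but it does not remove the gap for those who do leave.

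**Unfinished forms.** The questionnaires are still in development, so their administration may change. That makes the correction easy. It does not alter the timing already written in sections 9.3.3 and 12.1.2.

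**Conclusion.** The point holds in a narrow form. Followed as written, the plan yields a satisfaction result for completers only, and no specified analysis or reporting rule makes that visible. The figure may be overstated if residents who withdraw are less satisfied; that is plausible but not shown. With 10% lost and 80% satisfied among responders, both assumed, the bias lies between +8 and −2 points, and it widens in proportion to the share lost. I read participant satisfaction as applying to the intervention arm, since section 9.3.3 speaks of satisfaction with the intervention. The effect is confined to one descriptive implementation outcome. The primary, secondary and safety results do not change. This is a cheap improvement, not a defect that threatens the trial.

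**What to change.** 1. In section 9.2.5, add the short satisfaction questionnaire to the two already offered to intervention residents who stop early. It is offered before exit, so it is compatible with section 8.5, which needs no amendment.
2. In section 9.3.2, give the questionnaire at Visit 2 to intervention residents who remain. This alone would still miss earlier leavers, so it complements item 1. Keep a later contact for residents in hospital on the Visit 2 date, because section 9.2.5 drops the participant questionnaires for them.
3. Align sections 9.3.3 and 12.1.2 with this timing, and state there whether relatives of residents who died will be approached.
4. In section 11.4.2, report satisfaction with the number of responders out of all residents allocated to intervention, the response by exit status (completed, withdrew, died), and best- and worst-case bounds computed as (1 − a) × s + a and (1 − a) × s.

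The cost is one extra short form for residents who leave, at a contact that already exists, plus wording in a few sections while the form is still being written. Residents who die before Visit 2 will still be missing. The denominator and the bounds make that visible.
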